## Statistical plan

### Trial size

The minimal clinically important difference in internal carotid artery blood flow between evaluations at MAP 65 and 95 mmHg is estimated to be 15%. A power calculation indicated that at least 16 patients were required to detect a difference in internal carotid artery blood flow of 15% corresponding to about 24 ml/min with a standard deviation for the change of 31 ml/min in order to obtain a 5% significance level and a power of 80%. We plan to include 20 patients.

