### Statistical analysis

Analysis of the time points at MAP 65, 80, and 95 mmHg is by a repeated measure mixed model, fit by restricted maximum likelihood in a structured covariance model with intervention (MAP 65, 80, and 95 mmHg) as a fixed effect, and the individual variable as a random effect to account for the within-individual correlation of the data (Proc mixed; SAS 9.4, SAS Institute, Cary, NC, USA). If the overall effect of the intervention is significant, the changes between the levels of MAP will be evaluated with correction for multiple testing by the Tukey–Kramer Test for Post Hoc Analysis. Analysis of variables not normally distributed is after logarithmic transformation in order to obtain a normal distribution or by a Friedman test and if the test is significant changes are evaluated using Wilcoxon signed rank sum test with correction for multiple testing by the Tukey–Kramer Test for Post Hoc Analysis. Values are presented as mean  $\pm$  SD or median with interquartile range for not normally distributed data and statistical significance is set at  $P < 0.05$ . Figures are drawn in R for Windows (version 3.4.1) using the package ggplot2.

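### The minimum of 16 patients fits a single unadjusted paired test of MAP 65 against 95 mmHg, not the planned overall test with Tukey–Kramer correction, which needs about 19–20 if every pairwise change has an SD of 31 ml/min

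*SAP*

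**What the plan says.** Under Trial size, the SAP bases the sample size on one within-patient difference in internal carotid artery flow, "between evaluations at MAP 65 and 95 mmHg". It states: "A power calculation indicated that at least 16 patients were required to detect a difference in internal carotid artery blood flow of 15" per cent, "corresponding to about 24 ml/min with a standard deviation for the change of 31 ml/min", at a 5% significance level and 80% power. It then adds: "We plan to include 20 patients". That section mentions neither the intermediate MAP level nor multiplicity.

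Under Statistical analysis, MAP 65, 80 and 95 mmHg enter one mixed model, "fit by restricted maximum likelihood in a structured covariance model", with "the individual variable as a random effect to account for the within-individual correlation of the data". The pairwise rule is: "If the overall effect of the intervention is significant, the changes between the levels of MAP will be evaluated with correction for multiple testing", the correction being Tukey–Kramer. The comparison of 65 with 95 mmHg is not set apart from the other two.

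**The concern.** A sample size supports a stated power only for the test it was calculated for. Here the number is tied to one contrast at 5%, while the analysis tests that contrast only after a significant overall test and then against a stricter critical value. If the 16 comes from an unadjusted test, the 80% attached to it overstates the power of the planned procedure.

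The apparent reserve is also affected. Set against a minimum of 16, a planned 20 looks like room for four losses. Against the minimum for the planned test, there may be little or no room.

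**Working it through.** **Inputs.** From Trial size: difference 24 ml/min, SD of change 31 ml/min, 5%, 80%, minimum 16, planned 20. From Statistical analysis: three levels, overall test, then Tukey–Kramer. Two assumptions are added. Testing is two-sided, which is the reading that reproduces 16. The SD of 31 is that of the 65–95 change, since the SAP gives no SD for 65–80 or 80–95.

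**Step 1: the plan's own figure.** For a paired t-test, df = n − 1 and the noncentrality is (24/31)·√n.

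- n = 15: noncentrality 2.998, critical t 2.145, power 79.6%.
- n = 16: noncentrality 3.097, critical t 2.131, power 82.5%.

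So 16 is reproduced exactly, for a single unadjusted comparison. The same test with 20 patients has 90.7% power.

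**Step 2: the Tukey–Kramer step alone.** The critical value becomes q(0.95; 3, df)/√2, with the same noncentrality. With a pooled residual variance, df = 2(n − 1); with a standard error specific to the contrast, df = n − 1. At n = 16 the critical value is 2.465 (df 30) or 2.597 (df 15), a per-comparison level of 0.0196 or 0.0202.

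| n | Unadjusted paired t | Tukey, df 2(n − 1) | Tukey, df n − 1 |
|---|---|---|---|
| 16 | 82.5% | 73.3% | 68.9% |
| 18 | 87.2% | 79.3% | 75.6% |
| 19 | 89.1% | 81.9% | 78.5% |
| 20 | 90.7% | 84.2% | 81.2% |

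The loss comes from the multiplicity step, not from the mixed model: an unadjusted contrast with df 2(n − 1) has 85.0% power at n = 16.

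**Step 3: overall test plus Tukey–Kramer, SD 31 for every pair.** A plain random-individual model implies equal SDs of change. The residual variance is then 31²/2 = 480.5. Simulated power for 65 against 95 mmHg is given for a linear response (means 0, 12, 24) and a plateau (0, 24, 24).

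| n | Pooled variance, df 2(n − 1): linear / plateau | Contrast-specific SE, Wald F with (2, n − 1) df: linear / plateau |
|---|---|---|
| 16 | 71.9% / 73.0% | 67.6% / 68.1% |
| 18 | 78.2% / 79.1% | not run |
| 19 | 80.8% / 81.7% | not run |
| 20 | 83.2% / 83.9% | 80.0% / 81.0% |

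The pooled analysis therefore needs 19. The contrast-specific one needs 20, since at 19 the Tukey step alone gives only 78.5%. An exact Hotelling overall test, which the SAP does not name, gives 78.9% / 80.4% at n = 20, so a linear response would need 21.

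**Step 4: dependence on the missing SDs.** Keep 31 for 65–95 and vary the SD of both adjacent-level changes. Under pooling, the effective SD is the root mean square of the three: √((31² + 2·25²)/3) = 27.1 for 25, and √((31² + 2·36²)/3) = 34.4 for 36.

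| Adjacent SD (pooled variance) | n = 16: linear / plateau | n = 20: linear / plateau |
|---|---|---|
| 25 | 80.8% / 82.0% | 89.6% / 90.1% |
| 31 | 71.9% / 73.0% | 83.2% / 83.9% |
| 36 | 62.4% / 63.6% | 75.7% / 76.6% |

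At SD 36, 22 patients are needed (80.7% / 81.4%). Under pooling, 16 reach 80% if the adjacent SD is at most about 26, and 20 reach it if it is at most about 33. The gain at SD 25 arises only because unequal variances are pooled. With a contrast-specific standard error, adjacent SDs of 25, 31 or 36 leave power at 67.6–68.6% for n = 16 and 80.0–81.2% for n = 20.

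**Step 5: rounding of the inputs.** With a difference of 23.5–24.5 and an SD of 30.5–31.5, the unadjusted minimum is 15–17. With Tukey–Kramer alone it is 18–20 (df 2(n − 1)) or 19–21 (df n − 1). At the least favourable corner, with the overall test and a linear response, it is 21 or 22.

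**The case against.** The arithmetic behind 16 is correct, and sizing a trial on one key contrast while analysing all levels together is common. Trial size names the contrast and does not say that 16 refers to the Tukey-adjusted test. This stands as far as it goes: there is no calculation error. It does not remove the mismatch, because the SAP attaches 80% power to a test that its analysis section does not perform.

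The operative number is 20, and 20 meets the target under equal SDs. This stands, and it limits the point to wording.

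The size of the shortfall rests on SDs the SAP does not give; with a pooled variance and small adjacent-level SDs, 16 would be enough. This also stands, so the figures must carry their assumption. Equal SDs are nevertheless what a plain random-individual model implies, and with a contrast-specific standard error 16 falls short at every adjacent SD tried.

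Finally, the protocol, which is not shown, might name 65 against 95 mmHg as a single unadjusted primary comparison, and 16 would then be right. That is only a possibility; the SAP as written subjects every pairwise change to the correction.

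**Conclusion.** The concern holds, as a minor point. That the stated size and power belong to a different test from the planned one is certain from the SAP alone, given two-sided testing. How far they differ is conditional. With an SD of change of 31 ml/min for all pairs and complete data, the 80% attributed to 16 patients is about 68–73%, about 19–20 evaluable patients are needed, and the planned 20 give about 80–84%.

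The reserve is thin. With 18 evaluable patients, power is about 76–79% (75.6–79.3% for the Tukey step alone). The trial is not endangered under the equal-SD assumption; the stated justification needs correcting.

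**What to change.** Keep the analysis and the planned 20, and replace the sample-size sentence along these lines:

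> Sixteen patients suffice for a single unadjusted paired comparison of MAP 65 and 95 mmHg. With the planned overall test and Tukey–Kramer correction, and assuming an SD of change of 31 ml/min for all pairs, about 19–20 evaluable patients are needed, and the planned 20 give about 80–84% power.

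If the sponsor has SDs for the 65–80 and 80–95 mmHg changes, the figure should be recalculated with those and with the covariance structure named, because a pooled analysis is sensitive to both.

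The cost is wording only. The stated figure becomes slightly less favourable and rests on an SD assumption that the SAP does not support with data. No test, error rate or patient number changes.

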### Statistical analysis

Analysis of the time points at MAP 65, 80, and 95 mmHg is by a repeated measure mixed model, fit by restricted maximum likelihood in a structured covariance model with intervention (MAP 65, 80, and 95 mmHg) as a fixed effect, and the individual variable as a random effect to account for the within-individual correlation of the data (Proc mixed; SAS 9.4, SAS Institute, Cary, NC, USA). If the overall effect of the intervention is significant, the changes between the levels of MAP will be evaluated with correction for multiple testing by the Tukey–Kramer Test for Post Hoc Analysis. Analysis of variables not normally distributed is after logarithmic transformation in order to obtain a normal distribution or by a Friedman test and if the test is significant changes are evaluated using Wilcoxon signed rank sum test with correction for multiple testing by the Tukey–Kramer Test for Post Hoc Analysis. Values are presented as mean  $\pm$  SD or median with interquartile range for not normally distributed data and statistical significance is set at  $P < 0.05$ . Figures are drawn in R for Windows (version 3.4.1) using the package ggplot2.

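### Does leaving the covariance structure and degrees-of-freedom method unnamed leave the tests of the MAP changes too open?

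*SAP*

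**What the plan says.** The Statistical analysis section specifies a repeated-measures mixed model in Proc mixed (SAS 9.4), "fit by restricted maximum likelihood in a structured covariance model". MAP level (65, 80, 95 mmHg) is the fixed effect, with "the individual variable as a random effect to account for the within-individual correlation of the data". Testing is in two steps: "If the overall effect of the intervention is significant, the changes between the levels of MAP will be evaluated with correction for multiple testing" by Tukey–Kramer, and "statistical significance is set at" P < 0.05. No covariance type is named, and no method for the degrees of freedom.

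The Trial size section bases the number of patients on the 65 to 95 mmHg change alone: "a difference in internal carotid artery blood flow of 15% corresponding to about 24 ml/min", "with a standard deviation for the change of 31 ml/min". The minimum is 16 patients. "We plan to include 20 patients".

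**The concern.** The section fixes the estimator, the software, the overall test, the post hoc procedure and even the plotting package, yet leaves a category where the covariance model should be. More than one model fits the words:

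- **Reading A:** a random patient intercept with equal residuals. One pooled error variance serves all three changes.
- **Reading B:** each change has its own variance, either through level-specific residuals beside the random intercept or through an unstructured covariance.

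The overall test and the Tukey–Kramer comparisons both depend on this choice. The same data could therefore give different verdicts, and an analyst who tried both and kept the better would exceed the stated 5%. It also looks as if the choice decides whether 20 patients reach 80% power, because simulated power for the 65–95 change falls on either side of that figure.

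**Working it through.** **Inputs from the SAP:** change 24 ml/min, SD of the change 31 ml/min, 16 patients required, 20 planned, 5% level, three MAP levels. **Assumptions:** two-sided tests, complete data and, except in step 5, equal variance of the three changes. Except where varied in step 3, the mean at MAP 80 is taken as halfway (0/12/24).

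**1. The SAP's own figure.** A paired two-sided t-test with noncentrality (24/31)·√n gives power 79.6% at n = 15, 82.5% at n = 16 and 90.7% at n = 20. The minimum of 16 is reproduced. It belongs to a single uncorrected paired comparison.

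**2. Degrees of freedom and critical values at n = 20.** Reading A has (20 − 1)(3 − 1) = 38 degrees of freedom; Reading B has 20 − 1 = 19 for each change. The Tukey critical t is the studentized-range value for three means divided by √2. The standard error of the 65–95 change at SD 31 is 31/√20 = 6.93 ml/min. The smallest change that passes the Tukey step is then:

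- A: 2.439 × 6.93 = 16.9 ml/min
- B: 2.540 × 6.93 = 17.6 ml/min

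The difference is 0.7 ml/min, against a planned effect of 24.

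**3. Power and error** (the gated rows come from simulation):

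| | A: pooled | B: separate variances |
|---|---|---|
| Overall test, critical value on the F scale | 3.24 | 3.75 (Hotelling) |
| 65–95 power, Tukey step alone | 84.2% | 81.2% |
| 65–95 power after the overall test | 83.1% | 78.9% |
| Any-pair error, no effect | 4.4% | 4.3% |

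The two analyses disagree on 65–95 in 7.1% of trials. They disagree on at least one of the three pairs in 20.0%, but that count includes the two adjacent 12 ml/min changes, for which the trial was not sized and which have power of only about 25% and 23%.

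The contrast around 80% does not bear weight. The SAP's 80% was set for the uncorrected test in step 1, not for a gated, Tukey-corrected one. The 78.9% also depends on the assumed MAP 80 mean: power under B is 79.4% at 0/6/24 or 0/18/24, and about 80.4% at 0/0/24 or 0/24/24.

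**4. What choosing between them does to the error rate.** Choosing by AIC, blind to P values, gives an any-pair error of 4.6%. Counting a pair as significant whenever either analysis says so gives 5.5 to 5.7% in repeated simulation. An unstructured fit tested on an uncorrected 38 degrees of freedom gives 5.9% by itself.

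**5. Unequal variances (assumed; the SAP has no figure).** Under A the 65–95 standard error uses the mean of the three change variances, so it is off only if the 65–95 variance differs from that mean. Let a share f of 31² = 961 come from patients' differing linear slopes. Each adjacent change then has variance 961·f/4 + 961·(1 − f).

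- f = 30%: 72.1 + 672.7 = 744.8. The mean of the three is (2 × 744.8 + 961)/3 = 816.9. The pooled standard error is √(816.9/961) = 0.92 of the right one.
- f = 60%: 144.2 + 384.4 = 528.6. The mean is (2 × 528.6 + 961)/3 = 672.7, and the ratio is √(672.7/961) = 0.84.

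Gated 65–95 error under A is then 2.8% and 4.6%, against 1.7% under B. Disagreement on 65–95 is 9.0% and 12.3%, and picking the better gives an any-pair error of 5.8% and 6.6%. If instead the residual variance at MAP 80 is doubled, A is the conservative one for 65–95 (power 72% against 79%) but has more power for 65–80 (20% against 16%). Neither reading is better throughout.

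**The case for a change.** The strongest case for acting is that a prespecified analysis should let a reader confirm that the reported test was the planned one. Naming Proc mixed does not settle this, because the covariance and the default degrees of freedom depend on how the model is coded. The mention of a structured covariance beside the random effect can suggest a further residual structure. One sentence would close the gap and cost no patients.

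There is also a setting in which the pooled reading does poorly. If adjacent MAP levels correlate much more strongly than distant ones, its overall test has an error of 5.8% (correlations 0.84/0.84/0.70) or 8.2% (0.90/0.90/0.65). In the second case the change variances stand as 0.10 : 0.10 : 0.35, so the 65–95 variance is 0.35/0.183 = 1.9 times the pooled mean. The limit, reached when every patient's response is exactly linear (1 : 1 : 4), is 4/2 = 2, so this is close to the worst case possible.

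The omission stands as a fact. The rest is weaker. The two readings are not equally supported: the text gives the random individual effect the job of carrying the within-patient correlation, an unstructured fit sits awkwardly with the word structured, and level-specific residuals are nowhere mentioned. The correlation patterns are assumptions. They bear on which model is preferable, and nothing in the SAP shows that the pooled one is wrong here.

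**Conclusion.** This is a gap that an analyst fills sensibly, not an error in the method. The natural filling is a random patient intercept with equal residuals, which gives 38 degrees of freedom with complete data. The alternative is defensible as well. With complete data both give the same mean changes and, under equal variances, both keep the any-pair error below 5%. They differ by about 0.1 in the critical t and by about 7% of trials on the 65–95 comparison. Error above 5% under equal variances needs either a choice made after seeing the P values or an uncorrected small-sample test, and the SAP proposes neither.

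Making the unstructured fit primary would be a trade-off, not a gain: gated 65–95 power falls from 83.1% to 78.9% under equal variances, in return for protection against a covariance pattern for which the SAP gives no evidence. The sample size is untouched. The conclusion rests on complete data and on the three change variances not being far apart. If they were, the readings would differ more, but the SAP would still contain no wrong statement. No change to the plan follows.

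### The trial is sized on one uncorrected 65 v 95 comparison, but the analysis tests it behind both an overall-test gate and a Tukey–Kramer correction, which is stricter than three MAP levels require

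*SAP*

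**What the plan says.** **Trial size.** The comparison sized is internal carotid artery flow at MAP 65 against MAP 95, with a difference "corresponding to about 24 ml/min with a standard deviation for the change of 31 ml/min". From this, "at least 16 patients were required to detect a difference in internal carotid artery blood flow of 15" per cent, "in order to obtain a 5% significance level and a power of 80" per cent. Twenty patients are planned. Neither an overall test nor a multiplicity correction is mentioned.

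**Statistical analysis.** The mixed model has "intervention (MAP 65, 80, and 95 mmHg) as a fixed effect". Pairwise testing is then conditional: "If the overall effect of the intervention is significant, the changes between the levels of MAP will be evaluated with correction for multiple testing", the correction being Tukey–Kramer. Data that stay non-normal follow the same two-step pattern: "by a Friedman test and if the test is significant changes are evaluated using Wilcoxon signed rank sum test with correction for multiple testing", again by Tukey–Kramer. No reason is given for using both steps, and 65 v 95 has no special place among the three pairs.

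**The concern.** The comparison that sets the sample size and the comparison that will be tested are the same contrast under different rules. The sizing corresponds to one test at 5%. The analysis requires 65 v 95 to pass an overall test and then a corrected threshold, so the stated minimum of 16 does not deliver 80% power for the planned test.

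The second layer also adds nothing needed for error control. Tukey–Kramer covers all pairs without a gate. With three levels the gate also suffices alone: if two of the three pairwise null hypotheses are true, all three levels are equal, and the 5% overall test already guards that case; if only one is true, a single 5% test guards it. With four or more levels this argument would fail. At stake is power in a trial of 20 patients, for 65 v 95 and for the adjacent pairs that show where flow changes.

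**Working it through.** **Inputs from the SAP.** Difference 24 ml/min; SD of the paired change 31 ml/min; significance 5%; target power 80%; minimum n = 16; planned n = 20; three MAP levels.

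**Assumptions, not in the SAP.** Two-sided tests, normal data, complete data, equal variances of all pairwise differences (compound symmetry), and a MAP 80 mean anywhere between the means at the two ends.

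**1. The plan's own figure.** For a paired t-test the noncentrality is (24/31)·√n on n − 1 degrees of freedom.
- n = 15: power 79.6%.
- n = 16: noncentrality 0.774 × 4 = 3.10, power 82.5%.
- n = 20: power 90.7%.

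The smallest n reaching 80% is 16, as stated. The sizing is therefore consistent with one uncorrected 65 v 95 test.

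**2. Tukey–Kramer alone.** The critical t is q(0.95; 3, 2(n − 1))/√2, with noncentrality as above and 2(n − 1) degrees of freedom.
- n = 16: critical t 2.465, per-comparison level 0.0196, power 73.3%.
- n = 20: critical t 2.439, per-comparison level 0.0195, power 84.2%.

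**3. Gate and Tukey–Kramer together.** Simulation of n patients by three levels, residual SD 31/√2, overall F test on 2 and 2(n − 1) degrees of freedom. The first row of power figures in each pair uses level means (0, 12, 24), the second (0, 0, 24).

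| Power for 65 v 95 | As written | Tukey–Kramer alone | Gate + unadjusted pairs |
|---|---|---|---|
| n = 16, (0, 12, 24) | 71.9% | 73.3% | 74.6% |
| n = 16, (0, 0, 24) | 73.0% | 73.3% | 81.2% |
| n = 20, (0, 12, 24) | 83.1% | 84.1% | 85.0% |
| n = 20, (0, 0, 24) | 84.0% | 84.1% | 90.2% |

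- Cost of adding the gate to Tukey–Kramer: at most 73.3 − 71.9 = 1.4 points.
- Cost of adding Tukey–Kramer to the gate: from 85.0 − 83.1 = 1.9 to 81.2 − 73.0 = 8.2 points.

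**4. Adjacent pairs, n = 20.** For a true 12 ml/min: 25% as written, 25% with Tukey–Kramer alone, about 39% with gate plus unadjusted pairs. For a true 18 ml/min: about 56%, 57% and 70%. Across n = 16 and n = 20 the difference between the first and last figures is about 11-14 points.

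**5. Family-wise error.**

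| | As written | Tukey–Kramer alone | Gate + unadjusted pairs | Neither |
|---|---|---|---|---|
| All levels equal | 4.5% | 5.0% | 5.0% | 12% |
| One level differs | 2.0% | 2.0% | 5.0% | 5.0% |

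**6. Minimum n for the analysis as written.** By the formula in step 2, Tukey–Kramer alone gives 79.3% at n = 18 and 81.9% at n = 19. The gate can only lower these. At 18 the plan is thus below 80%; at 19, taking off the largest gate cost, 81.9 − 1.4 = 80.5%. Direct simulation agrees: 78.0-79.0% at 18 and 80.6-81.5% at 19. The minimum is about 19.

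**7. Sensitivity to the error term.** If correlation decays with MAP distance (autoregressive, correlation 0.5-0.9, assumed) but the model pools error as under compound symmetry, an uncorrected 65 v 95 test has a type I error of 8-10% at n = 20. A paired t-test on the same data stays at 5%. With separate paired tests, power as written at n = 20 is about 79-81%, and the gate costs Tukey–Kramer up to about 3.4 points.

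**The case against.** The strongest reply is that the procedure is valid and conventional: it names the levels, the test and the correction, and keeps family-wise error below 5%. That stands, and this point does not say otherwise.

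A reader might infer that stacking the two layers is what costs every comparison its power. The figures do not support that. Without the gate, Tukey–Kramer has practically the same power for adjacent pairs (25% v 25% at a true 12 ml/min) and the same 2.0% error when one level differs. Those features belong to Tukey–Kramer. Removing only the gate recovers little; the larger gains need Tukey–Kramer to go, which is partly a choice of method and gives up simultaneous intervals.

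A reader might also infer that the trial is underpowered. At the planned 20, 65 v 95 keeps 83-84% (79-81% with separate paired tests). The 72-73% applies at 16, which is the stated minimum, not the planned size. The adjacent pairs have no stated power target.

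Finally, an uncorrected test with a pooled error term could be less safe than the present text (8-10% error in step 7). That stands too, and it determines how the fix must be worded.

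**Conclusion.** The point holds as a mismatch between sizing and analysis and as a modest, avoidable loss of efficiency. The SAP sizes one uncorrected contrast and tests it under two layers where one would hold 5%. At the stated minimum of 16, power for 65 v 95 is about 72-73% as written, against 82.5% for the test that reproduces that minimum; at 20 it is 83-84% against 90.7%. These figures assume two-sided testing, complete normal data, compound symmetry and an intermediate MAP 80 mean. The closed-test argument rests on there being exactly three levels and on a correct error term for each pair. Validity is not in question. It is worth correcting because the change is cheap.

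**What to change.** 1. **Internal carotid flow.** Name 65 v 95 as the single primary comparison, tested directly at two-sided 5% without gate or correction. Use a paired t-test, or a model covariance that lets the variances of the differences vary; do not use a pooled compound-symmetry error. This is the test that gives 82.5% at 16 and 90.7% at 20. Label the other two pairs secondary. The primary test then carries its own 5%, separate from the secondary family.
2. **Remaining comparisons.** Keep one layer and say which. Either use the overall test at 5% followed by unadjusted 5% pairs with pair-specific errors, noting that with three levels this is a closed test (more power), or use Tukey–Kramer without the gate (simultaneous intervals, little power gained).
3. **Non-parametric branch.** Apply the same rule: Friedman test at 5%, then unadjusted Wilcoxon pairs.
4. **If the text is kept.** Restate the 80% minimum in Trial size as about 19 patients. The planned 20 still meets it under the assumptions above, with little margin if separate paired tests are used.

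The cost is a few sentences of SAP wording, with no extra patients or data. If Tukey–Kramer is dropped, the pairwise intervals are no longer simultaneous.
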